**Table 1. Candidate Covariates for Inverse Probability Weight Models for Enrollment and Adherence**

Demographics	Comorbidities	Labs / Vital Signs	Other	Survey PROMs

 
▪ Age
 
▪ Gender
 
▪ Insurance Status
 
▪ Race/Ethnicity
 
▪ SES
 
▪ Primary Language
 
	
 
▪ Comorbidity Index (e.g., Charlson, Elixhauser)
 
▪ CVD/CHD
 
▪ CV Risk Score
 
▪ Smoking
 
	
 
▪ Baseline BP
 
▪ BMI
 
▪ eGFR
 
▪ Creatinine
 
	
 
▪ BP Meds
 
▪ Med Count
 
▪ Utilization
 
▪ Clinical characteristics (e.g., % BP control)
 
▪ Provider characteristics (e.g., Specialty)
 
▪ Calendar time
 
	
 
▪ Self-Rated Health
 
▪ Prior BP Monitoring
 
▪ Education
 
▪ Employment
 
▪ Life Satisfaction
 
▪ Self-Efficacy
 

In the second stage of analysis we will apply the weights to generalized linear regression models to estimate the effect of per-protocol treatment on study outcomes. This model will be restricted to study patients who followed their assigned protocol (MTM visit if intervention, no MTM visit if best practice). By weighting individuals by their inverse probability of enrollment/adherence, we essentially create a pseudo-population for analysis, in which factors that were unbalanced in those who were enrolled/adherent vs. those who were not are no longer unbalanced. The effect estimate from this weighted model then represents the unbiased effect of actual, per-protocol treatment on BP outcomes.

The validity of inverse probability weighting depends on the assumptions of consistency, positivity, correct model specification, and exchangeability. *Consistency* (the outcome observed for a given patient is consistent with their true outcome given their actual treatment status) is generally assumed to hold in this context. The *positivity* assumption requires a non-zero probability of receiving every level of exposure (telehealth, best practice) for every combination of covariate histories, which can be evaluated empirically. If we detect violations (or near-violations) of positivity, we will report these in tabular form, attempt to diagnose these as deterministic (a group of patients who would never be treated) or stochastic (random zeroes due to insufficient sample size), and implement one or more of the following approaches: 1) restrict the study population to patients with some likelihood of receiving telehealth; 2) re-specify the models and/or confounding variables, and/or truncate weights, in an effort to achieve acceptable balance

in bias due to nonpositivity vs. confounding; 3) modify the definition of treatment; and/or 4) use alternative estimation methods which are less sensitive to nonpositivity (e.g., g-computation, g-estimation of structural nested models, targeted maximum likelihood estimation). The potential for *model misspecification* to bias results can be mitigated by conducting a series of sensitivity analyses similar to those demonstrated in Cole and Hernan, with the objective of optimizing the bias-variance tradeoff.

*Exchangeability* refers to the assumption that comparison groups (telehealth vs. best practice) are ‘exchangeable’ with respect to distributions of risk factors for outcomes (BP), possibly conditional on measured covariates. This assumption is more generally recognized as ‘no unmeasured confounding,’ which applies to most epidemiologic studies. Although this assumption is untestable, we believe it will be reasonably defensible for several reasons. First, the model for enrollment is likely to be largely dependent on clinic-level treatment assignment and patient clinical characteristics, which would have been available to the provider, and will be available for analysis. Second, although the model for treatment adherence is more likely to be driven by factors that are not routinely captured in clinical data, we will have several relevant patient-reported survey measures (see Table 1) available for study participants. Third, we will implement bias analyses as well as upper/lower bounds for the per-protocol effect, which will provide a range of plausible values under various sets of realistic assumptions to complement the per-protocol effect estimate.

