#### **5.A.1. Current infrastructure and policies**

1. Accurate BP measurement is promoted by the consistent use of validated oscillometric BP monitors (Omron HEM 907XL) according to a standard nursing protocol. The protocol includes proper cuff size, proper positioning of the patient, and requires a repeat BP measurement after 5 minutes of rest when the initial BP is elevated. Both automated EHR alert and physical reminders are used to prompt repeat BP measurement at the same visit when the initial BP is elevated. (See Appendix A for Nursing BP Measurement Protocol)
2. Patients have access to no-cost blood pressure recheck visits with an MA and consultations with a clinical pharmacist trained in medication therapy management (MTM) to follow up on uncontrolled BP at clinic encounters. MTM pharmacist consultations are face-to-face visits in the patient's primary care clinic and generally do not include ongoing follow up. Patients may self-refer or can be referred by a PCP, MA, or RN.
3. A hypertension registry is used to enumerate the patient population with hypertension (controlled and uncontrolled). The registry is used to identify and contact patients who need follow-up for uncontrolled hypertension. (See Appendix D for Hypertension Registry Standard Operating Procedure, Appendix E for Hypertension Registry Technical Specifications)
4. PCPs use an evidence-based hypertension treatment algorithm that promotes low-cost generic medication and single-pill combination therapy, when possible. If BP is uncontrolled at an MA visit, the MA may consult a registered nurse (RN) or MTM pharmacist. RNs and pharmacists have separate protocols to adjust hypertension

treatment. If the RN or pharmacist is unavailable at the time of the MA visit, the patient may be contacted by telephone and/or scheduled for a return visit to the PCP. (See Appendix B for MTM Hypertension Protocol, Appendix C for ICSI Guidelines for Hypertension Management)

5. PCP and clinic performance on BP control is measured with monthly feedback. Clinic managers have access to monthly reports and routinely download and distribute them to PCPs. BP control is a high priority performance measure, with open comparison within and between clinics.
6. Home BP monitoring may be encouraged by individual clinicians, but is not supported by infrastructure or policies.

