### **5.A.2. Hypertension care processes**

The study will create and enhance automated EHR tools to promote the following iterative process:

1. Recognition of uncontrolled BP and high BP study criteria at primary care encounters
2. Therapeutic action to address uncontrolled BP at primary care encounters (may include medication adjustment, addressing non-adherence, and counseling on lifestyle changes)
3. Follow-up visits to re-assess uncontrolled BP within 2-4 weeks. Follow-up visits may be scheduled with a PCP, MA, or MTM pharmacist.

Blood pressure in the ambulatory primary care setting at HealthPartners is measured by the MA during the rooming process for a clinic appointment, or at the time of a nurse blood pressure check using an electronic, automated monitor. If an initial BP  $\geq 140/90$  is entered into the EHR vital signs field it will trigger an automated BPA pop up to remind the MA to repeat the BP if the initial BP is elevated after 5 minutes of rest. If the study inclusion/exclusion criteria are met on the repeat BP, a new BPA appears on the computer screen prompting the MA to open and pend an order for hypertension follow up. The default follow-up interval is 2 weeks unless the BP is  $\geq 180/110$  in which case the default follow up interval is set to 1 week. The type of provider for the follow up visits defaults to nurse, PCP, or MTM depending on the clinic randomization. All defaults can be changed by the MA or at provider discretion if desired by clicking a different options within the order, but the patient is enrolled by any signed order.

Implementation and fidelity to hypertension care processes will be measured as described in Section 7.D and Table 2 using EHR vital sign, diagnosis, current medications, medication order, and encounter data stored and linked to individual study patient IDs and encounters. The study will foster reliable processes in all study clinics through training, measurement, and feedback to improve the consistency with which the hypertension follow up orders are pending, signed, scheduled, and completed.

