Suggestions from the focus groups and analyses of study data were used to modify our previous telehealth care intervention in the following ways. **1)** The qualifications of pharmacists to treat hypertension and the collaborative nature of their work with the patient's PCP will be emphasized. **2)** In order to remove barriers for team care, home BP data will be transmitted and stored in the HealthPartners Epic EHR, rather than in a password-protected third-party Web site. Home BP data will be maintained in a flowsheet that is separate from BP measured during clinic visits. **3)** Trajectories of BP during the Hyperlink study showed maximum BP lowering after an average of about 3 months, with little additional BP lowering during the remainder of the 6 months of intensive intervention and 6 additional months of maintenance. Therefore, rather than having a fixed duration, the telehealth care intervention will be flexible and tailored to individual patients' needs. **4)** Patients will have several options for transmitting home BP data (further details below). In any case, patients will be given their own BP monitor for long-term use.

Telehealth care clinics will offer best-practice clinic-based care, but eligible patients in these clinics will be referred for telehealth care with systematic home BP telemonitoring and BP management through the MTM pharmacist. Referrals will take place using the same hypertension follow up orders used for clinic-based care, but the default will be MTM pharmacist follow-up. There is currently a high rate of appointment completion following referral to MTM pharmacists. As in the clinic-based care group, the study will foster reliable processes to improve the consistency with which the order set is used and uncontrolled BP is re-assessed by an MTM pharmacist within 4 weeks. Following an initial face-to-face intake visit, the MTM pharmacist and patient will communicate by telephone or secure e-mail (according to patient preference) at regular intervals, adjusting medication using established care protocols and collaborative practice agreements until BP control has been achieved. Pharmacists will also support lifestyle changes and adherence to treatment. Other CV risk factors including smoking, hyperlipidemia, hyperglycemia in diabetic patients, and use of aspirin will be addressed as needed using evidence-based protocols, since this is the customary practice of MTM pharmacists at HealthPartners.

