**Figure 1. Directed acyclic graph representing the primary study aims.**

For the per-protocol analysis, we are interested in estimating the effect of **A** on **Y** (as opposed to the ITT effect of randomized assignment **Z** on **Y**). The DAG above shows multiple backdoor paths from **A** to **Y**: 1) through **L**, 2) through conditioning on the collider **S** and then through **L**, and 3) through **U**. To account for these sources of potential bias, we will use inverse probability weighting to estimate the per-protocol effect of the telehealth intervention on blood pressure outcomes.

Inverse probability weighting can be used to estimate unbiased measures of effect where selection bias or confounding is present, under specific assumptions. To estimate the per-protocol effect of the telehealth intervention on BP

outcomes, we will use a two-stage modeling process. In the first stage, we will construct logistic regression models for 1) enrollment, and 2) patient adherence to the assigned treatment. Candidate variables for inclusion in these models will be specified *a priori*; from these candidate variables, models will be optimized using Lasso selection based on the Bayesian Information Criterion. Individual probabilities of enrollment/adherence can then be calculated based on each patient's vector of covariate values. Stabilized inverse probability weights will then be calculated, combined (enrollment IPW \* adherence IPW), and diagnostically evaluated as previously described.

Based on contextual knowledge and preliminary summaries of the study population, we anticipate that the variables listed in Table 1 (in addition to clinic assignment of telehealth vs. best practice) may be associated with enrollment and/or treatment adherence. All will be considered for model inclusion. Patient-reported outcome measures (PROMs) will be available only for patients who are enrolled (and complete a survey), thus, these will be considered for the patient adherence model, but not the model for enrollment.

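### The per-protocol rule sets no time window for the MTM visit and names no post-enrollment BP in its weights, so it can select clinic-based patients on follow-up SBP and cannot be called unbiased

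*Combined protocol and SAP*

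**What the plan says.** Section 10.A.2 sets out a two-stage per-protocol analysis to complement the ITT result.

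- **Weights.** There is one logistic model for enrollment and one for adherence. "Individual probabilities of enrollment/adherence can then be calculated based on each patient's vector of covariate values". The candidate covariate table in that section lists baseline BP and no later BP. Medication, medication count and utilization items carry no date.
- **Analysis set.** "This model will be restricted to study patients who followed their assigned protocol (MTM visit if intervention, no MTM visit if best practice". No window or number of visits is given, and the text does not say which SBP values enter the second-stage model. It then describes the weighted estimate as unbiased.
- **Clinic-based care.** Section 5.A.1 gives these patients access to "consultations with a clinical pharmacist trained in medication therapy management (MTM) to follow up on uncontrolled BP at clinic encounters". It adds: "If BP is uncontrolled at an MA visit, the MA may consult a registered nurse (RN) or MTM pharmacist". Section 5.A.2 says: "Follow-up visits may be scheduled with a PCP, MA, or MTM pharmacist".
- **Outcome data.** Section 7.A collects SBP at all qualifying encounters for 24 months.

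**The concern.** In the clinic-based arm, an MTM visit can be the response to a high BP found after enrollment. Removing patients who had one can therefore remove patients because their follow-up SBP was high. Weights built from enrollment-time values cannot undo that, because two patients with the same baseline BP differ in their chance of removal according to what happened later. The causal diagram in 10.A.2 has paths through measured prognostic factors, enrollment and unmeasured characteristics, but the listed paths do not include follow-up SBP leading to treatment received.

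Telehealth has a related gap. Nothing says that SBP recorded before a patient's first MTM visit is kept out of the treated experience.

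Two things are at stake. One is the claim of an unbiased effect of treatment received. The other is consistency: a clinic-based patient sent to the pharmacist under section 5.A has received care which that arm allows, yet is off protocol under 10.A.2. Section 10.A.2 itself says the ITT comparison may be biased, so readers are likely to lean on this analysis.

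**Working it through.** The plan states no figure for this analysis, so there is none to reproduce. The checks below size the error in the clinic-based mean.

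**Inputs from section 10.A.3:** SD of all SBP 20.4; patient ICC .28; index SBP mean 159.9, SD 16.1. Between-patient variance is 20.4² × .28 = 116.5 (SD 10.8). Within-patient SD is 20.4 × √.72 = 17.3.

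**Trigger:** SBP of 140 or more, the level that sections 4.C and 5.A.2 use for a repeat measurement.

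**Assumptions, not in the documents:** referral chance p per triggering reading of 5%, 10% or 20%; usual follow-up mean of 148.

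**1. One reading, by hand.**
- z = (140 − 148)/20.4 = −0.392, so P(SBP ≥ 140) = 0.653 and the normal density at z is 0.369.
- Error in the triggering reading among patients kept = −p × 20.4 × 0.369 / (1 − 0.653p). At p = .20 this is −1.507/0.869 = −1.73 mm Hg.
- A later reading shares only the patient component: .28 × −1.73 = −0.49.
- The index SBP carries 116.5/16.1² = 116.5/259.2 = 45% of the patient variance, so weighting on it leaves about 55%: 0.55 × −0.49 = −0.27.

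Simulation of this case gave −0.49 unweighted and −0.27 weighted. The triggering reading is affected far more than later ones, so the choice of SBP values matters.

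**2. Three readings, then a 12-month SBP.** One million simulated clinic-based patients, with an MTM effect of −5 mm Hg assumed once referred. The target is the 12-month mean had nobody in the arm had an MTM visit.

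| p | Ever MTM | Unweighted | Weighted on baseline SBP | Weighted on follow-up SBP |
|---|---|---|---|---|
| 5% | 9% | −0.33 | −0.18 | 0.00 |
| 10% | 18% | −0.69 | −0.38 | −0.01 |
| 20% | 34% | −1.46 | −0.77 | +0.03 |

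**3. Three readings, all averaged.** Patients were selected on two entry SBPs of 150 or more from an assumed population mean of 140, with no treatment effect.

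| p | Dropped | Weighted on baseline SBP |
|---|---|---|
| 5% | 10% | −0.48 |
| 10% | 20% | −0.98 |
| 20% | 36% | −2.11 |

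In the same setup, if only earlier readings trigger MTM and only the last is analyzed, the error is −0.13 at 5% and −0.54 at 20%.

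**4. Level or slope.** In setup 3 at p = 10%, a rerun gave errors of −0.95, −0.95 and −0.94 at the three visits. The shift is in level and the post-enrollment slope barely changes.

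**5. Direction.** These runs use baseline weighting and three readings.
- Referral at 10% whatever the BP: error 0.
- Half the patients engaged, with SBP 5 mm Hg lower and twice the chance of MTM; referral 10% if high, 5% if not: −0.12.
- Engaged patients 8 mm Hg lower with three times the chance: +0.18 with the same referral rates, +0.79 with 10% at every reading.

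**The case against.** **Silence is not a statement.** The plan does not say that a visit at any time counts, that weights use baseline values only, or that one visit fixes the status of earlier SBP. Several candidate covariates are undated, and the positivity paragraph speaks of covariate histories. This stands as a limit on wording: the supportable claim is that no window is set and no post-enrollment BP is named. It does not rescue the rule, because an analyst following the text has no window to apply, and undated utilization or medication items do not replace follow-up SBP.

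**The direction is not certain.** Patients may self-refer, and order defaults can be changed at the enrollment visit, where baseline BP is available to the weights. The telehealth restriction adds selection of unknown sign, which was not sized. This stands.

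**The size is assumption-driven.** Referral rates have no source in the documents. In setup 3 the simulated index SBP is 164.6 (SD 11.3), against the plan's 159.9 (SD 16.1). This stands, and is why ranges are given.

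**Safeguards exist.** Section 10.A.2 makes validity conditional on assumptions, calls exchangeability untestable, and promises sensitivity analyses, bias analyses and bounds. None is specified for this mechanism, and g-methods appear only as a remedy for nonpositivity.

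**Conclusion.** The point holds as a weakness in a supportive analysis. As written, adherence can depend on follow-up SBP in the clinic-based arm and the named weights do not correct for that, so the claim of an unbiased estimate is not supported.

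If referral follows high BP, the clinic-based mean is likely too low. For p of 5-20% and three readings, the error is about 0.1-0.8 mm Hg for a later or 12-month SBP, and about 0.5-2.1 mm Hg if all readings, including the triggering ones, are averaged.

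A reader might infer that the clinic-based arm must look too good, and that a known share of the hypothesized 5 mm Hg telehealth advantage is lost. The documents do not support that. They give no referral rate, and engaged self-referral or selection in telehealth could shrink or reverse the error. Moreover, the 5 mm Hg in section 10.A is a difference in slope, while the error found is in level. It would enter the contrast directly only if the second-stage model compares means or change from index, which the plan leaves open. The ITT primary result is unaffected.

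**What to change.** In section 10.A.2:

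1. Keep each patient until the first deviation from the assigned protocol and censor SBP from that point. State by when a telehealth patient with no MTM visit counts as having deviated. Section 5.B already has a time target ("uncontrolled BP is re-assessed by an MTM pharmacist within 4 weeks"), but it is not linked to this analysis.
2. Replace the single adherence probability with time-updated inverse-probability-of-censoring weights that include the most recent clinic SBP and visit history. Date every covariate.
3. State which SBP values enter the second stage, and that SBP recorded before the first MTM visit does not count as treated.
4. Reconcile the rule that clinic-based patients have no MTM visit with sections 5.A.1 and 5.A.2, which allow one.
5. Drop the unqualified claim of unbiasedness, and specify the promised bias analyses and bounds for this mechanism.

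A fixed early adherence window, with only later SBP analyzed, can serve as a sensitivity analysis. It would count clinic-based patients who see the pharmacist after the window as adherent, which departs from the stated aim of estimating the effect had everyone followed the protocol.

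The cost is SAP wording, more analysis work on EHR data already extracted, and more variable weights.

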### 10.A.2. Per Protocol Analysis Plan

Given the pragmatic, unblinded, cluster-randomized study design, there is potential in this study for otherwise-eligible patients to not be enrolled, and for enrolled patients to subsequently seek treatment interventions (including no treatment) outside of their assigned protocol. Furthermore, we would like to know what the impact of actual receipt of the intervention (as opposed to clinic-level assignment) has on study outcomes. Therefore it will be desirable to conduct a per-protocol analysis (average effect of telehealth vs. best practice, had everyone followed the trial protocol) to complement the intention to treat (ITT) results of the primary analysis. Preliminary data suggests that the ITT approach in this study may be subject to bias due to 1) differential likelihood of enrollment based on provider knowledge of treatment assignment, and/or 2) differential self-selection of patients following through with the assigned treatment intervention. Because these processes operate post-randomization, the randomization scheme cannot ensure confounder balance by enrollment or treatment status, and the study population can be considered as analogous to an observational cohort.

Directed acyclic graphs (DAGs) have been used to depict causal relationships and illustrate potential sources of bias in epidemiologic studies. Briefly, DAGs consist of nodes (e.g., treatment, outcome, other variables) presented in temporal sequence and connected by arrows, which indicate potential causal pathways. If there is no arrow connecting two nodes, it can be assumed that no causal relationship exists. Where 'backdoor' paths can be identified, estimation of causal effects may be biased For this study a DAG might be drawn as depicted in Figure 1, where:

- **Z** is randomized treatment assignment;
- **S=1** represents selection (enrollment) into the study;
- **A** is actual treatment receipt (patient adherence to assigned intervention);
- **Y** represents BP-related study outcomes;
- **L** is a vector of observed patient prognostic factors (e.g., age, comorbidities);
- **U** represents a vector of (possibly unmeasured) patient characteristics predictive of adherence to the assigned intervention protocol.

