#### **14.B. Potential risks to subjects**

Potential risks to subjects relate to the treatment of hypertension and consist principally of adverse events related to medications, which can potentially be severe or even fatal. However, all treatment in the study in both intervention groups is evidence-based and limited to FDA-approved treatment. Although patients in the telehealth group may be treated with greater numbers and higher doses of antihypertensive therapy, previous telehealth trials with pharmacist or nurse management have not reported greater adverse events in the telehealth group. In the previous telehealth trial conducted by this research team there were several more episodes of hypotension in the telehealth group than in the usual care group, although this difference was not statistically significant. All such episodes occurred in patients with diabetes or kidney disease who had a lower BP treatment goal (<130/80 mm Hg) than is the goal in this study (<140/90 mm Hg). Therefore, the risks of participating in the study are considered minimal and no greater than those incurred through routine treatment of hypertension. We have described below the methods used to minimize this risk.

Additional risks to patients are also minimal and include principally the risk of violation of confidentiality. Measures to minimize these risks are also discussed below.

Study participants may choose alternative treatments and procedures with their treating clinician. Participants in the telehealth group are free to decline telemonitoring or any component of the telehealth care intervention.

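### The per-protocol adherence rule (MTM visit in the telehealth arm, no MTM visit in the clinic-based arm) does not match either arm's protocol, so the analysis does not estimate its stated effect

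*Combined protocol and SAP*

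**What the plan says.** Section 10.A.2 adds a per-protocol analysis to complement the intention-to-treat (ITT) result. Its target is the "average effect of telehealth vs. best practice, had everyone followed the trial protocol". Logistic models for enrollment and for adherence give stabilized inverse probability weights, and then "we will apply the weights to generalized linear regression models to estimate the effect of per-protocol treatment on study outcomes". That second-stage model is "restricted to study patients who followed their assigned protocol (MTM visit if intervention, no MTM visit if best practice"). The plan says the weighted estimate "then represents the unbiased effect of actual, per-protocol treatment on BP outcomes".

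Section 5 describes what each arm is meant to receive. For clinic-based care, section 5.A.1 lists no-cost "consultations with a clinical pharmacist trained in medication therapy management (MTM) to follow up on uncontrolled BP at clinic encounters", by self-referral or staff referral, and says this element is in place in all primary care clinics. Section 5.A.2 asks for reassessment of uncontrolled BP within 2-4 weeks and adds: "Follow-up visits may be scheduled with a PCP, MA, or MTM pharmacist". For telehealth care, section 3 says the arm differs through systematic home BP telemonitoring and home-based care coordinated by a pharmacist. Section 5.B.1 has the pharmacist find out at the intake visit whether the patient is willing to monitor at home, and section 14.B says participants are "free to decline telemonitoring or any component of the telehealth care intervention".

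**The concern.** A per-protocol analysis has to define adherence by the protocol that each arm was given. Here one marker, an MTM visit, serves both arms with opposite signs. In the clinic-based arm the marker is an offered part of the care. In the telehealth arm it is the entry to the care and not the care itself.

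Section 10.A.2 warns that the ITT result may be biased by differential enrollment and by self-selection after enrollment. Readers will therefore look to this analysis for the effect of telehealth as received. If the adherence indicator is wrong, the label on that estimate is wrong however well the weights are built.

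**Working it through.** **1. Apply the rule to individual patients.** The plan gives no numerical result for this analysis, so there is no figure to reproduce. The check sets the rule beside the arms' own descriptions.

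| Patient | Under the section 10.A.2 rule | Under the arm's own description |
|---|---|---|
| Clinic-based, BP follow-up done by the MTM pharmacist | Excluded | Within protocol (5.A.1 element 2; 5.A.2 step 3) |
| Clinic-based, no BP follow-up at all | Adherent | Outside protocol: 5.A.2 asks for reassessment, and the opening of 10.A.2 names no treatment among departures |
| Telehealth, one MTM intake, telemonitoring declined | Adherent | Did not receive the feature that defines the arm (3; 5.B.1; 14.B) |
| Telehealth, intake plus telemonitoring | Adherent | Adherent |

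Three of the four rows disagree. The second row matters mainly for patients who miss reassessment and return later for another reason, because section 7.A takes systolic BP (SBP) from routine encounters only.

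**2. Ask whether the planned safeguards reach this.** The weights model the probability of the same adherence indicator, so they inherit its definition. Section 10.A.2 takes consistency as generally holding. Changing the treatment definition appears only as one of several responses to a positivity problem. The bias analyses and bounds are offered in support of exchangeability. None of these is a planned check of the definition.

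**3. Illustrate the size.** Assume confounding is fully removed. Measure SBP reduction relative to a clinic-based patient with no MTM visit.

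- D = 5 mm Hg, the difference in Hypothesis 1.1, taken as the true effect of full telehealth against best practice as designed.
- q = share of clinic-based patients with an MTM visit (assumed 0 to 0.3).
- m = SBP benefit of an MTM visit alone (assumed 0 to 4 mm Hg).
- p = share of telehealth-arm MTM attenders who take up telehealth (assumed 0.6 to 1.0).

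Best practice as designed averages a reduction of q·m, so full telehealth averages D + q·m. Under the rule, the retained clinic-based patients average 0 and the retained telehealth patients average p(D + q·m) + (1 − p)m. Hence

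estimate = p(D + q·m) + (1 − p)m.

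- p = 0.8, q = 0, m = 0: 0.8 × 5 = 4.0 mm Hg, too small.
- p = 1, q = 0.2, m = 4: 5 + 0.8 = 5.8 mm Hg, too large.
- Lowest in the range (p = 0.6, m = 0, any q): 0.6 × 5 = 3.0 mm Hg.
- Highest in the range (p = 1, q = 0.3, m = 4): 5 + 1.2 = 6.2 mm Hg.

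Counting decliners as treated pulls the estimate down towards m. Dropping permitted MTM users from the clinic-based arm widens the contrast by q·m when p = 1. The two act in opposite directions. The illustration leaves out the clinic-based patients with no follow-up, for whom the documents give nothing to work from.

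**4. Variance.** Section 10.A.2 names only a family of regression models. The H1.1 model in section 10.A carries a clinic random effect. With 100 patients per clinic, leaving clinic out would understate the standard error by √(1 + 99 × ICC): 1.14 at the ICC of .003 observed in section 10.A.3, and 1.41 and 1.99 at the conservative .01 and .03 assumed there. Restricting to adherent patients lowers the number per clinic and so the factor. This is a reason to state the structure. It does not show that clustering will be ignored.

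**The case against.** The best defence is that the MTM visit is a workable proxy. Section 3 says clinic-based care relies mainly on the physician and medical assistant. The default follow-up provider depends on randomization (5.A.2), with MTM the telehealth default (5.B). MTM visits in routine care usually have no ongoing follow-up (5.A.1). The Reach measure in section 10.B takes PCP follow-up as the clinic-based step and pharmacist or NP follow-up as the telehealth step. This explains where the rule came from. However, the plan does not call it a proxy, and the Reach measure itself requires PCP follow-up, whereas the rule requires nothing.

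A second objection is that declining telemonitoring is as permitted as seeing the pharmacist. The two permissions differ in kind: the MTM consultation is a listed element of best-practice care, while section 14.B records a freedom to refuse.

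A third is that the word unbiased is conditional, since the plan goes on to list the assumptions of weighting. That is fair, but those assumptions concern confounding and model form. They do not turn one contrast into another.

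Some stronger readings are tempting and do not hold:

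- *Any pharmacist visit counts as telehealth.* Only in telehealth clinics; in clinic-based clinics it leads to exclusion.
- *The rule flatters telehealth.* Removing clinic-based pharmacist users could raise or lower the control mean, depending on who is referred. The other error dilutes the effect, and weighting may offset part of either.
- *The analysis has immortal-time bias.* The plan does not say which readings enter or when the outcome clock starts. SBP is continuous, so nobody must stay event-free to qualify, and readings before the visit would tend to dilute a telehealth benefit.
- *The model ignores clustering.* It is unspecified, which is a different fault.

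**Conclusion.** The mismatch between the adherence rule and the two arms' protocols stands on the text alone. The analysis as written estimates any MTM visit in telehealth clinics against no MTM visit in clinic-based clinics. That is a legitimate contrast, but it is not the one stated at the start of section 10.A.2, and the estimate should not be presented as the unbiased per-protocol effect.

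The net direction and size of the error are unknown. The range of 3.0 to 6.2 mm Hg around a true 5.0 rests on assumed values of p, q and m and on perfect confounding control. It shows only that the discrepancy could matter in either direction.

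A reader might infer that the trial's main result is compromised. It is not: the rule enters only this complementary analysis, and the ITT tests of H1.1 and H1.2 do not use it. Tables 2 and 3 and the appendices are not in the text reviewed, but section 10.A.2 does not refer to them for adherence.

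**What to change.** Before analysis, amend section 10.A.2 as follows.

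- Define adherence from each arm's own section 5 protocol. Clinic-based: a completed BP follow-up with any permitted provider, MTM pharmacist included, and no study telemonitoring. Telehealth: an MTM intake plus evidence of home telemonitoring, such as at least one entered or transmitted home reading.
- Use one stated window for both arms, long enough for equipment to be set up after intake. Section 5.B aims for the MTM reassessment within 4 weeks and section 5.B.1 has equipment ordered at intake, so a 4-week window that required a home reading could class patients who do take up telehealth as non-adherent.
- State which SBP readings count relative to that window.
- State that the weighted model accounts for clustering by randomization unit (19 units, section 3) and for repeated readings within patients.
- Keep the MTM-visit rule as a sensitivity analysis, labelled MTM visit versus none. If nothing else changes, rename the estimand in those terms and drop the claim that it is the unbiased per-protocol effect.

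The cost is mainly SAP wording. Sections 5.B and 5.B.4 say home BP goes to an EHR flowsheet and telehealth processes are measured from EHR data, so the inputs should exist, although the exact fields could not be checked here. Fewer telehealth patients will count as adherent, so intervals will be somewhat wider.
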